## **8.1. Efficacy Assessments**

The following procedures will be conducted as part of exploratory assessments.

### **8.1.1. Body Weight**

Weight will be recorded using a calibrated scale (with the same scale used if possible for the duration of the study) reporting weight in either pounds (lb.) or kilograms (kg), and accuracy to the nearest 0.2 lb. (or 0.1 kg); ie, the device must be able to distinguish a difference between 150.4 lb. (68.4 kg) versus 150.2 lb. (68.3 kg). The scale must be placed on a stable, flat surface.

Weight measurement should be taken under the following conditions:

- After void of urine;
- After removal of shoes, bulky layers of clothing and jackets so that only light clothing remains;
- While remaining still during the measurement.

### **8.1.2. Imaging Assessment**

#### **8.1.2.1. CT Scan**

CT scans will be acquired throughout the study to monitor the tumor burden and evaluate the Lumbar Skeletal Muscle Index, in addition to other potential exploratory muscle quality parameters. The standard process to obtain serial CT scans will be outlined in an Image Acquisition Manual. The sites will be provided with guidance on obtaining CT images of the chest, abdomen, and pelvis that meet the quality requirement of this study.

If a CT scan was performed within 3 weeks prior to the Screening visit and meets the quality and anatomical requirements, then a CT scan at screening is not needed. If a CT scan was not performed prior to Screening, a CT scan should be performed after other eligibility criteria (such as medical history, diagnosis) have been confirmed. The CT scan may be performed without receipt of safety laboratory and GDF-15 sample results. If a CT scan is being performed at the Week 6 or Week 12 visit as part of the standard of care, then an

additional CT scan is not needed as long as CT scan quality matches the requirements outlined in the Image Acquisition Manual.

Monitoring of the tumor burden will be performed by the local imaging site following standard RECIST 1.1 criteria (outlined in [Appendix 17](#)). The RECIST 1.1 categorization is to be entered in the CRF after each scan.

CT scans will also be required to be sent to a central imaging review facility for evaluation of the Lumbar Skeletal Muscle Index and exploratory measures of muscle quality. Central image review is not a complete medical review of the participant and will not include any tumor assessments. If, during the central review process, an unexpected observation is identified and this finding could, in the opinion of the central reviewer, have a significant health or reproductive consequence, this finding may be shared with the study sponsor for disclosure to the principal investigator (PI). All follow up testing and final diagnosis will be left to the discretion of the medical professionals at the site or those with an existing physician participant relationship. The PI will be responsible for reporting any AEs identified from incidental findings as described in the [AE](#) reporting section. Identification of such incidental findings during the central review process should not be expected, and the site maintains responsibility for performing a general safety review of all images as per site protocols.

### **8.1.3. Patient-Reported Outcomes (Cohort 1)**

All patient-reported outcome (PRO) assessments are implemented on an ePRO device (hand-held device for home use and tablet for clinic use) and completed by study participants at home, or at the clinic, following a schedule of assessments as per the [SoA](#) and [Table 2](#). Every effort should be made to have the study participant complete all patient-reported outcome assessments before any other clinical assessments that take place at the clinical site.

The site user guide will be provided separately.

**Table 2. Patient Reported Outcomes for Cohort 1**

Patient Reported Outcome (PRO) Measure Planned	Frequency	Assessment	Number of Questions	Completion Time
CCI				
PRO-CTCAE selected items: taste change, decreased appetite, fatigue, nausea, vomiting	Conducted at clinic visits on Day 1 (Baseline), Week 3, Week 6, Week 9, Week 12 and Week 18	At the clinic	9	~3 minutes
Patient Global Impression of Severity (PGI-S) (1 item: appetite)	Conducted at clinic visits on Day 1 (Baseline), Week 3, Week 6, Week 9, Week 12 and Week 18		1	
Patient Global Impression of Change (PGI-C) (2 items: appetite and fatigue)	Conducted at clinic visits on Week 12 and Week 18		2	
PROMIS-Fatigue 7a (“Past 7 days” recall version)	Conducted at clinic visits on Day 1 (Baseline), Week 6, Week 12, and Week 18		7	~14 minutes
PROMIS-Physical Function 8c (no recall version)	Conducted at clinic visits on Day 1 (Baseline), Week 6, Week 12, and Week 18		8	
FAACT	Conducted at clinic visits on Day 1 (Baseline), Week 6, Week 12, and Week 18		39	

CCI

### 8.1.3.2. Patient-Reported Outcomes Version of the Common Terminology Criteria for Adverse Events (PRO-CTCAETM)

Initiated and sponsored by the US National Cancer Institute, the PRO-CTCAE (Appendix 9) is a patient-reported outcome measure developed to evaluate symptomatic toxicity in patients enrolled in cancer clinical trials. It was designed to complement the Common Terminology Criteria for Adverse Events (CTCAE), the standard lexicon for investigator or clinician-reported adverse events in cancer trials. The PRO-CTCAE item library is composed of 124 self-report items reflecting 78 symptomatic adverse events drawn from the CTCAE arranged by organs and systems. Each adverse event is assessed relative to one or more attributes that include the presence/absence/amount (P), frequency (F), severity (S), and interference (I) with usual or daily activities. PRO-CTCAE provides a systematic yet flexible tool for descriptive reporting of symptomatic treatment side effects in cancer clinical trials. PRO-CTCAE data will be collected and analyzed and reported separately from CTCAE AE data and will not be reconciled with each other. Adverse events for this study will be assessed, recorded, and reported in the standard manner with investigators using CTCAE.

From the 78 symptomatic adverse events, the following were selected to be administered in the study, each with a 7-day recall period: taste changes (S), decreased appetite (S and I), nausea (S and F), vomiting (S and F), fatigue (S and I).

#### **8.1.3.3. Patient's Global Impression of Severity (PGI-S)**

The Patient's Global Impression of Severity (PGI-S) ([Appendix 10](#)) is a single item measure that asks the study participants to evaluate their current severity of lack of appetite on a 5-point verbal response scale that ranges from "None" to "Very severe".

The PGI-S is recommended by Food and Drug Administration (FDA) for use as an anchor measure to generate an appropriate threshold that represents meaningful within-individual change in the target patient population.

#### **8.1.3.4. Patient's Global Impression of Change (PGI-C)**

The PGI-C ([Appendix 11](#)) is a single item measure that asks study participants to rate the overall change in their level of appetite and fatigue since they started the study on a 7-point verbal rating scales that ranges from "Much better" to "Much worse".

The PGI-C is recommended by FDA for use as an anchor measure to generate an appropriate threshold that represents meaningful within-individual change in the target patient population.

#### **8.1.3.5. PROMIS – Fatigue (version 7a)**

The PROMIS Fatigue 7a ([Appendix 12](#)) is a self-reported measure that assesses a range of symptoms in the past 7 days from mild subjective feelings of tiredness to an overwhelming, debilitating, and sustained sense of exhaustion that likely decreases one's ability to execute daily activities and function normally in family or social roles.

The short form 7A consists of 7 items that study participants will rate from 1: "Never" to 5: "Always". A global raw score ranging from 7 to 35 is calculated and can be translated into a T-score (Mean = 50, standard deviation (SD) = 10) using the applicable score conversion table provided in the PROMIS User's Manual.

#### **8.1.3.6. PROMIS – Physical Function (version 8c)**

The PROMIS Physical Function short form 8C ([Appendix 13](#)) is a self-reported 8-item measure that assesses capability rather than actual performance of physical activities. It includes the functioning of one's upper extremities (dexterity) and lower extremities (walking and mobility), as well as instrumental activities of daily living. A single Physical Function capability score is obtained from a short form. A global raw score ranging from 8 to 40 is calculated and can be translated into a T-score (Mean = 50, SD = 10) using the applicable score conversion table provided in the PROMIS User's Manual.

### **8.1.3.7. Functional Assessment of Anorexia-Cachexia Therapy (FAACT)**

The Functional Assessment of Anorexia-Cachexia Therapy (FAACT) ([Appendix 14](#)) measures combines the Functional Assessment of Cancer Therapy - General (FACT-G) core instrument and anorexia and cachexia subscale (ACS).

FACT-G is a summated score of 27 items pertaining to physical well-being (7 items), emotional well-being (6 items), functional well-being (7 items), and social well-being (7 items) in the past 7 days. Each of the items uses a 5-point (0 to 4) scale. ACS is a 12-item summated scale containing items specific to patients' perceptions of appetite and weight, also using the 5-point scale. Adding the 12 ACS items to the FACT-G produces the 39-item Functional Assessment of Anorexia-Cachexia Therapy (FAACT). Higher scores are associated with a higher health-related quality of life. For additional details regarding scoring refer to FACIT User's Manual.

CCI

## **8.2. Safety Assessments**

Planned time points for all safety assessments are provided in the [SoA](#). Unscheduled clinical laboratory measurements, imaging and other safety assessments may be obtained at any time during the study as part of standard of care or to assess any perceived safety concerns.

Injection site reactions will be assessed as part of standard safety/AE monitoring. Additional assessments may be conducted at investigator discretion and/or until any symptoms resolve. Injection site reactions may include but are not limited to: erythema, induration, ecchymosis, pain, and pruritus. The size and severity of injection site reactions will be assessed and documented. If deemed appropriate by the investigator, a consultation with a dermatologist may be performed. Documentation of a reaction may include items such as investigator notes, photographs, dermatologist report and/or clinic notes.

In addition to the safety monitoring as detailed in the [SoA](#), safety monitoring for this open-label Phase 1b study will include monthly reviews of all available data to screen for trends in AEs, vital signs, ECGs and safety laboratories.

### **8.2.1. Physical Examinations**

Physical examinations may be conducted by a physician, trained physician's assistant, or nurse practitioner as acceptable according to local regulation.

A full physical examination will include, at a minimum, head, ears, eyes, nose, mouth, skin, heart and lung examinations, lymph nodes, and gastrointestinal, musculoskeletal, and neurological systems. and weight will also be measured and recorded, (height will be measured at screening only).

An abbreviated physical examination will be focused on general appearance, the respiratory and cardiovascular systems, and subject-reported symptoms.

A full physical examination will be conducted at screening only; Abbreviated physical exams planned at all other clinic visits, however full exams may be performed for findings during previous exam, new/open AEs, or at investigator discretion. Investigators should pay special attention to clinical signs related to previous serious illnesses.

### **8.2.2. Eastern Cooperative Oncology Group (ECOG)**

Assessment of ECOG performance status (see [Appendix 16](#)) may be conducted by a physician, trained physician's assistant, or nurse practitioner as acceptable according to local regulation.

### **8.2.3. Vital Signs**

Blood pressure and pulse rate will be assessed at times specified in the [SoA](#).

Blood pressure and pulse rate measurements will be assessed supine with a completely automated device. Manual techniques will be used only if an automated device is not available. On Day 1, blood pressure and pulse rate will be measured in triplicate, approximately 2 to 4 minutes apart. The average of these triplicate measurements collected prior to dosing on Day 1, will serve as each participant's baseline value. At all other visits, a single measurement will be collected. Blood pressure and pulse rate measurements should be preceded by at least 5 minutes of rest for the participant in a quiet setting without distractions (eg, television, cell phones).

### **8.2.4. Electrocardiograms**

Standard 12-Lead ECGs should be collected at times specified in the [SoA](#) section of this protocol. All scheduled ECGs should be performed after the participant has rested quietly for at least 10 minutes in a supine position. Participants should be in a quiet environment and not speak during the resting period or measurement.

On Day 1, triplicate standard 12-lead ECGs will be obtained approximately 2 to 4 minutes apart. The average of the triplicate ECG measurements collected prior to dosing on Day 1 will serve as each participant's baseline value. At all other visits, a single standard 12-lead ECG will be collected. To ensure safety of the participants, a qualified individual at the investigator site will make comparisons to baseline measurements. Additional ECG monitoring will occur if a) any postdose QTc interval is increased by  $\geq 60$  msec from the baseline **and** is  $>470$  msec; or b) an absolute QTc value is  $\geq 500$  msec for any scheduled ECG. If either of these conditions occurs, then a single ECG measurement must be repeated at least hourly until QTc values from 2 successive ECGs fall below the threshold value that triggered the repeat measurement. In addition, if verified QTc values continue to exceed the criteria above, immediate correction for reversible causes including electrolyte abnormalities, hypoxia and concomitant medications for drugs with the potential to prolong the corrected QT (Fridericia method) (QTcF) interval should be performed. A cardiologist should be consulted if QTc intervals do not return to less than the criterion listed above after 8 hours of monitoring (or sooner, at the discretion of the investigator).

In some cases, it may be appropriate to repeat abnormal ECGs to rule out improper lead placement as contributing to the ECG abnormality. It is important that leads be placed in the same positions each time in order to achieve precise ECG recordings. If a machine-read QTc value is prolonged, as defined above, repeat measurements may not be necessary if a qualified medical provider's interpretation determines that the QTc values are in the acceptable range.

ECG values of potential clinical concern are listed in [Appendix 7](#).

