#### **9.4.2.1. Electrocardiogram Analyses**

Changes from baseline for the ECG parameters QT interval, heart rate, QTc interval, PR interval, and QRS complex will be summarized by time (and cohort, if applicable).

The number (%) of participants with maximum postdose QTc values and maximum increases from baseline in the following categories will be tabulated (by cohort, if applicable):

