## 10.7. Appendix 7: ECG Findings of Potential Clinical Concern

ECG Findings That May Qualify as Adverse Events (AEs)

 
Marked sinus bradycardia (rate <40 bpm) lasting minutes.
 
New PR interval prolongation >280 msec.
 
New prolongation of QTcF to >480 msec (absolute) or by <math>\geq</math>60 msec from baseline.
 
New-onset atrial flutter or fibrillation, with controlled ventricular response rate: ie, rate <120 bpm.
 
New-onset type I second-degree (Wenckebach) atrioventricular (AV) block of >30 seconds' duration.
 
Frequent premature ventricular complexes (PVCs), triplets, or short intervals (<30 seconds) of consecutive ventricular complexes.
 

ECG Findings That May Qualify as Serious Adverse Events (SAEs)

 
QTcF prolongation >500 msec.
 
New ST-T changes suggestive of myocardial ischemia.
 
New-onset left bundle branch block (QRS >120 msec).
 
New-onset right bundle branch block (QRS >120 msec).
 
Symptomatic bradycardia.
 
Asystole: 
 
In awake, symptom-free patients in sinus rhythm, with documented periods of asystole <math>\geq</math>3.0 seconds or any escape rate <40 bpm, or with an escape rhythm that is below the AV node;
 
In awake, symptom-free patients with atrial fibrillation and bradycardia with 1 or more pauses of at least 5 seconds or longer;
 
Atrial flutter or fibrillation, with rapid ventricular response rate: rapid = rate >120 bpm.
 
 
 
Sustained supraventricular tachycardia (rate >120 bpm) ("sustained" = short duration with relevant symptoms or lasting >1 minute).
 
Ventricular rhythms >30 seconds' duration, including idioventricular rhythm (rate
 

<40 bpm), accelerated idioventricular rhythm (40< x <100), and monomorphic/polymorphic ventricular tachycardia >100 bpm (such as torsades de pointes).

- Type II second-degree (Mobitz II) AV block.
- Complete (third-degree) heart block.

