3.1.2. Laboratory Data

Safety laboratory tests (hematology, chemistry, urine testing and other clinical laboratory tests) will be performed on Day 1 and Weeks 3, 6, 9, 12, 15, 18 and 24.

To determine if there are any clinically significant laboratory abnormalities, the safety tests will be assessed against the criteria specified in the sponsor reporting standards. The assessment will take into account whether each participant's baseline test result is within or outside the laboratory reference range for the particular laboratory parameter.

Baseline for all laboratory measurements is defined as the last result prior to dosing on Day 1.

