6.1.3. Vital Signs

Absolute values and changes from baseline in supine systolic and diastolic blood pressure and pulse rate will be summarised by treatment and time point, according to sponsor reporting standards using the safety population defined in Section 4. Baseline is as defined in Section 3.1.3.

Individual plots of change from baseline systolic and diastolic blood pressure and pulse rate, versus time, will be produced with all participants on the same plot, paged by treatment. Separate colours will be used for each participant with a black solid line added for the mean. Maximum decrease from baseline for supine systolic and diastolic blood pressures and maximum increase from baseline for supine pulse will be summarised by treatment, according to sponsor reporting standards.

Maximum absolute values and changes from baseline for supine vital signs will also be summarised descriptively by treatment using categories as defined in Appendix 4. Numbers and percentages of participants meeting the categorical criteria will be provided. All planned and unplanned post dose time points will be counted in these categorical summaries. All values meeting the criteria of potential clinical concern will be listed.

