6.1.4. Electrocardiogram (ECG)

Absolute values and changes from baseline in QT, heart rate, QTcF, PR and QRS will be summarised by treatment and time point using sponsor reporting standards using the safety population defined in Section 4. Tables will be paged by parameter. Baseline is as defined in Section 3.1.4.

Individual plots of change from baseline QT, heart rate and QTcF, versus time, will be produced with all participants on the same plot, paged by treatment. Separate colours will be used for each participant with a black solid line added for the mean. Maximum increase from baseline for QTcF will be summarised by treatment, according to sponsor reporting standards.

Maximum absolute values and changes from baseline for QTcF, PR and QRS will also be summarised descriptively by treatment using categories as defined in Appendix 4. Numbers and percentages of participants meeting the categorical criteria will be provided. All planned and unplanned postdose timepoints will be counted in these categorical summaries. All values meeting the criteria of potential clinical concern will be listed.

Listings of participants with any single post dose value > 500 msec will also be produced for QT.

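### The absolute-value ECG and vital-sign classes count worst post-dose values without showing whether the participant was already in that class on Day 1

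*Protocol*

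**What the plan says.** **Baseline.** For ECGs, Protocol 8.2.4 states: "The average of the triplicate ECG measurements collected prior to dosing on Day 1 will serve as" the participant's baseline. For blood pressure and pulse, Protocol 8.2.3 states: "The average of these triplicate measurements collected prior to dosing on Day 1, will serve as" the baseline. SAP 3.1.3 and 3.1.4 repeat both definitions. Every other visit has a single reading. The SAP schedules seven such visits after the first dose: Weeks 3, 6, 9, 12, 15, 18 and 24.

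**Counting.** Protocol 9.4.2.1: "The number (%) of participants with maximum postdose QTc values and maximum increases from baseline in the following categories will be tabulated". SAP 6.1.4: "Maximum absolute values and changes from baseline for QTcF, PR and QRS will also be summarised descriptively by treatment using categories" set out in Appendix 4. SAP 6.1.3: "Maximum absolute values and changes from baseline for supine vital signs will also be summarised descriptively by treatment using categories" from the same appendix. Both SAP sections count scheduled and unscheduled post-dose readings alike. The absolute rows of Appendix 4 carry no baseline term:
- QTcF >470 to 480, >480 to 500, and >500 msec
- PR >=300 and QRS >=140 ms
- systolic <90 and diastolic <50 mm Hg
- pulse <40 or >120 bpm

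**Where baseline is used.** Appendix 4 has separate change classes for QTcF, PR, QRS, systolic and diastolic pressure, and the PR change class is split by whether baseline exceeds 200. Pulse has no change class, but SAP 3.1.3 and 6.1.3 summarise its maximum increase from baseline. For laboratory data, SAP 3.1.2 takes into account whether the participant's "baseline test result is within or outside the laboratory reference range for the particular laboratory parameter".

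**Eligibility.** Protocol 5.1 and 5.2 set no numeric limit on QTcF, PR, QRS, pulse or low blood pressure. Exclusion 16 concerns uncontrolled high pressure. Exclusion 13 covers named cardiovascular conditions and ongoing dysrhythmia of CTCAE Grade 2 or above. Exclusion 4 leaves other conditions to the investigator's judgment.

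**The concern.** ECG and vital-sign findings are part of the primary endpoint, and the study has no control arm. A reader who sees one participant in eight in the QRS >=140 row has no background rate to set against it. The only reference is that participant's own Day 1 value, which the row does not show. Someone who entered with a wide QRS and left with the same QRS is counted exactly like someone whose QRS widened during treatment.

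The counts may be read when Cohort 1 data inform the dose level or frequency for the optional Cohort 2 (Protocol 4.1), and they may be reproduced in an interim analysis (SAP 7.2). The screening ECG and vital signs need not be reported (Protocol 9.4.4), so the Day 1 triplicate is the main pre-dose record.

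**Working it through.** The plan states no event rate, alpha or power for these tables, so there is no figure to reproduce. The check is a reading of the rules, followed by illustrations of size.

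**1. Reading the rules.** Take a participant with Day 1 mean QRS 150 ms and every later reading near 150. In Appendix 4 the absolute row (>=140) counts this participant and the change row (>=50% increase, that is >=225 ms) does not. Nothing in the absolute row marks the participant as already at 150.

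**2. Weight of one participant.** The safety population is everyone dosed, about 8 per cohort (Protocol 9.2 and 9.3). One participant is 1/8 = 12.5 percentage points.

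**3. Chance that a cohort contains such a participant.** The prevalence p of at least one absolute class on Day 1 is not in the documents and is assumed. P(at least one of 8) = 1 - (1 - p)^8.

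| Assumed p | P(at least one of 8) |
|---|---|
| 2% | 0.15 |
| 5% | 0.34 |
| 10% | 0.57 |
| 20% | 0.83 |

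A Day 1 abnormality alone adds nothing. It must persist or recur in a post-dose reading.

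**4. Chance that a stable participant is counted, with no drug effect.** Assumptions: the true value is constant, within-person errors are independent and normal, baseline is the mean of 3 readings, and there are 7 single post-dose readings. The true values and SDs are also assumed.

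| Stable true value | Assumed SD | Absolute row | P(counted) | Change row | P(counted) |
|---|---|---|---|---|---|
| QTcF 475 | 6 / 10 / 15 | >470 | about 1.00 throughout | increase >30 | 0.00 / 0.03 / 0.22 |
| QRS 150 | 4 / 8 | >=140 | 1.00 / 1.00 | increase >=50% | 0.00 / 0.00 |
| SBP 88 | 6 / 10 | <90 | 0.999 / 0.998 | fall >=30 | 0.00 / 0.03 |

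As a check, for QTcF 475 and SD 15: P(max >470) = 1 - Φ(-5/15)^7 = 1 - 0.369^7 = 0.999.

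**5. What a baseline split would show.** For the same QTcF 475 participant, the chance of appearing as newly above 470 (baseline mean <=470 and post-dose maximum >470) is 0.07 / 0.19 / 0.28 at SD 6 / 10 / 15, against about 1.00 in the present row.

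**6. What a baseline split would not remove.**
- A stable participant at 460 would appear as newly above 470 with probability 0.29 / 0.67 / 0.76, because seven single readings are compared with the threshold.
- The 475 participant exceeds 480 at least once with probability 0.796 / 0.924 / 0.960. P(baseline mean <=480) = Φ(5√3/SD) = 0.926 / 0.807 / 0.718. Their product, 0.74 / 0.75 / 0.69, is the chance of appearing as newly above 480 from noise alone. A cross-tabulation would usually at least show that this person started above 470.

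**The case against.** The best defence is that these are literal descriptions of post-dose maxima in a descriptive study, and that the rest of the output lets a reader recover the baseline. Much of that stands.

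- **Baseline is used.** A reader might infer that the plan collects the triplicate baseline and then ignores it. The SAP does not support that. It summarises absolute values and changes by time point, plots each participant's change for blood pressure, pulse, QT, heart rate and QTcF, lists flagged values, and has change classes for five parameters. With about 8 people, most cases can be separated by hand. What remains is that these are separate outputs: a change row does not say whether the person in the absolute row was already there.
- **The rows do not attribute.** A reader might also infer that pre-existing disease is being reported as a drug effect. Neither document calls these counts treatment-emergent. That label belongs to adverse events, and SAP 3.1.1 leaves out events that began before the first dose.
- **The documents do not contradict themselves.** Protocol Appendix 7 lists "New prolongation of QTcF to" above 480 msec, but it is guidance on what may qualify as an adverse event, and it also lists QTcF above 500 without requiring that it be new. The laboratory rule in SAP 3.1.2 is a useful precedent, and a different convention for ECGs is not an error.
- **Eligibility screens some cases.** Exclusions 4 and 13 will remove some such participants, although they set no limit on the measurements themselves.
- **An unconditional count is a defensible conservative display.** Counting only new cases would lose worsening within a class. QTcF rising from 501 to 529 (+28) stays in the top class and below the >30 change class. Systolic pressure falling from 89 to 65 (-24) stays in <90 and below the >=30 change class.

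**Conclusion.** The point holds for the absolute-value classes only, and it is minor. As specified, those rows cannot distinguish a new abnormality from one present on Day 1 that persists, and in a cohort of about 8 each such participant is worth 12.5 percentage points. One sixth (16.7 points) would use the approximately 6 completers as denominator, but the safety population is everyone dosed. Pulse is the weakest case, since it has no change class.

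The reading of the rules needs no assumptions. How often the problem would arise depends on a Day 1 prevalence that the documents do not give, and the simulated probabilities depend on assumed true values and within-person SDs. No hypothesis test or statistical decision rule is affected, because SAP 5.1 plans none. The consequence is confined to how descriptive safety counts will be read. The documents do not support the stronger conclusion that the present counts are wrong and should be replaced by counts of new cases.

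**What to change.** In SAP 6.1.3, 6.1.4 and Appendix 4, and for QTc in Protocol 9.4.2.1:

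1. Keep the unconditional worst-post-dose counts, the change-from-baseline classes and the listings.
2. For each absolute class, add a cross-tabulation of Day 1 class (triplicate mean) by worst post-dose class. Show participants who newly enter a class or move to a worse one separately from those already in it at baseline.
3. Add a footnote that baseline is a mean of three readings and the post-dose value is the extreme of at least seven scheduled single readings if all visits are attended, so moves close to a threshold may be measurement noise.

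The cost is SAP wording and one extra table layout. No new data, visits or participants are needed. The drawback is that the newly entering cells will still hold some stable participants near a threshold, so the change rows and individual listings should be read beside them.
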